### **4.0 PATIENT ELIGIBILITY**

### 4.1 Inclusion Criteria

- 4.1.1 Diagnosed with cancer, stage 1-4.
- 4.1.2 Completed taxane- or platinum-based chemotherapy, vinca alkaloids, or bortezomib at least three months (90 days) ago. Current use of anti-estrogen therapy, Herceptin, or PARP inhibitors is okay.

- 4.1.3 Clinical diagnosis of chemotherapy-induced peripheral neuropathy by clinician. This will be based on symptom history (paresthesias, dysesthesias, allodynia), loss of deep tendon reflexes, decreased vibratory sensation, or the presence of symmetrical stocking-glove numbness or paresthesias beginning after neurotoxic chemotherapy.
- 4.1.4 Self-reported average neuropathic pain score of at least 4 on a 10-point scale over the past 1 month.
- 4.1.5 Age ≥ 18 years
- 4.1.6 Concomitant use of analgesics is permitted if the dose has been stable for at least 2 weeks prior to study enrollment (no new analgesics have been added, discontinued, or changed in the 2 weeks prior to randomization).
- 4.1.7 Written informed consent obtained from subject and ability for subject to comply with the requirements of the study.

### 4.2 Exclusion Criteria

- 4.2.1 Syphilis, alcoholic neuropathy, diabetic neuropathy, neurological disorders, brain injury, or stroke, as assessed by the treating physician.
- 4.2.2 Neuropathy related to abnormal TSH or B12 levels as assessed by treating physician.
- 4.2.3 Current severe depression, suicidal ideation, bipolar disease, alcohol abuse, or major eating disorder, as assessed by the treating physician.
- 4.2.4 Currently participating in another CIPN-targeted program or trial.
- 4.2.5 Participated in a non-pharmacologic therapy specifically for the treatment of chemotherapy-induced peripheral neuropathy, including Scrambler Therapy, mindfulness meditation, or other mind-body activities within 14 days (2 weeks) prior to randomization.

### **5.0 TREATMENT PLAN**

### 5.1. Treatment Administration

Patients will be randomized 1:1 to one of the following regimens:

- Arm A: Continuous wear of Voxx HPT Socks for 2 weeks, followed by continuous wear of placebo socks for 2 weeks (separated by a 2-week washout period)
- Arm B: Continuous wear of placebo socks for 2 weeks, followed by continuous wear of Voxx HPT Socks for 2 weeks (separated by a 2-week washout period)

Voxx HPT Socks are commercially-available, FDA-exempt compression socks that are drug and electrical free. The Voxx HPT proprietary pattern is woven into a sock that is made of 70% cotton, 25% polyester, 3% spandex, and 2% nylon. Placebo socks will be made of the same fabric and will be identical in appearance to the HPT socks.

Prior to each 2-week treatment window, patients will be provided with 6 pairs of Voxx HPT socks or placebo socks. The investigator and patient will be blinded to treatment assignment between Voxx HPT first versus placebo first.

Patients will be asked to wear the socks continuously during both waking and sleeping hours, except when showering, bathing, or swimming. The socks should only be worn by the patient and should not be shared with other members of the household.

Both the Voxx HPT Socks and the placebo socks can be washed on delicate cycle and worn repeatedly.

Patients will be asked to keep a daily record of approximately how many hours the socks were worn, and whether the socks were worn while sleeping.

### 5.2 Method of Assigning Subjects to Treatment Groups

Study participants will be randomized 1:1 to the two treatment arms of the study in random block sizes of 4 and 6 subjects. Randomization will occur after patients' study eligibility has been confirmed.

### 5.3 Blinding

As this is a double-blind study, the patient and all but two members of the study team (Team Lead and Team Manager) will be blinded to treatment arm assignment.

The following study procedures will be in place to ensure double-blind administration of study treatments:

- The Team Lead and Team Manager will remain the only unblinded members of the study team and will be responsible for participant randomization.
- Access to the randomization code will be strictly controlled.
- The Team Lead or Team Manager will be responsible for the distribution of Voxx HPT socks versus placebo socks to the study coordinator(s), who will then distribute them to the patients.
- Unblinded study staff will not administer patient assessments.
- The Voxx HPT Socks and placebo socks will be identical in design to maintain the blind.
- Packaging and labeling of Voxx HPT Socks and placebo socks will be identical to maintain the blind.

### 5.4 Concomitant Therapy

Concomitant medications of interest will be recorded at screening using chart abstractions and patient self-report. Concomitant use of analgesics is permitted if the dose has been stable for at least 2 weeks prior to study enrollment. Concomitant medications of interest will also be abstracted from medical record at T0, T1, and T2.

Current participation in another CIPN-targeted program or trial is not allowed.

### 5.5 Duration of Study Participation

The study duration per subject will be up to 10 weeks, with up to 1 month of screening and 6 weeks of treatment (including the 2-week washout period).

### **6.0 STUDY PROCEDURES**

### 6.1 Screening Procedures

Assessments performed exclusively to determine eligibility for this study will be done only after obtaining informed consent.

All screening procedures must be performed within 30 days prior to T0 (baseline) unless otherwise stated. The screening procedures include:

### 6.1.1 Pre-screening

Study patients will be identified by study staff, pre-screening physician clinics, and by physician referral. Additionally, the Deep 6 Cohort Builder will be used to generate lists of potentially eligible patients who have been diagnosed with cancer, stage 1-4. Eligible patients will have completed chemotherapy at least three months (90 days) prior to prescreening and have a clinical diagnosis of chemotherapy-induced neuropathy. d. A member of the patient's treatment team will introduce the study in person, by email, or by phone, or the study team will contact the patient using the CSMC Research Interest Letter.

### 6.1.2 Informed Consent

### 6.1.2.1 In-Person Consenting

For patients who are recruited during a clinic visit, the MD-Investigator or other approved consenter will briefly introduce the study. If the patient is interested, the consent documents will be presented electronically on an iPad or on paper (based on the patient's preference). In-person electronic consenting and paper consenting procedures are outlined below.

### 6.1.2.1.1 In-Person Electronic Consenting via RedCap

The consent document (will be presented on an iPad and subjects will have the option of providing an electronic signature supported by the RedCap application. The MD-Investigator or other approved consenter will go through the regular consent process and document their discussion. Then the iPad will be transferred to the patient who will view the informed consent form. After reviewing the form, the patient will have the option to sign at the time of the clinic visit, take the consent home and return for consent or consent online from home (see Section 6.1.2.2), or decline study participation. The consenter will electronically sign ICF. Due to the low-risk nature of this study, patients will be permitted to consent on the same day. All consenting procedures are followed for online or paper consenting, including time to review consent, time to ask questions, the patient will not be rushed or coerced, the patient will be informed of the voluntary nature of research, and all other options will be discussed. All patients will be given a signed copy of the consent form and a study contact card.

### 6.1.2.1.2 In-Person Paper Consenting

If the patient prefers not to view the consent form electronically, a paper version of the consent form will be presented. The MD-Investigator or other approved consenter will go through the regular consent process and document their discussion by utilizing the approved discussion checklist. After reviewing the consent form, the patient will have the option to sign at the time of the clinic visit, take the consent home and return for consent or consent online from home (see Section 6.1.2.2), or decline study participation. Due to the low-risk nature of this study, patients will be

permitted to consent on the same day. All consenting procedures are followed for online or paper consenting, including: time to review consent, time to ask questions, the patient will not be rushed or coerced, the patient will be informed of the voluntary nature of research, and all other options will be discussed. All patients will be given a signed copy of the consent form.

### 6.1.2.2 Phone Consenting

In other cases, the MD-Investigator may introduce the study and then ask the patient if they would like to be contacted with more details. The MD-Investigator will notify study staff approved to consent to this protocol. If the patient is interested, study staff will obtain verification of the potential participant's identity by collecting at least two Electronic Health Record (EHR) identifiers, e.g., name, date of birth, social security number, address, email address, etc., and go through the regular consent process.. This discussion will be documented. The link to the secured consent will be emailed to the patient via RedCap. The patient will have the option to sign electronically via RedCap, return to the clinic to discuss and sign the consent in person with study staff, or decline study participation. Due to the low-risk nature of this study, patients will be permitted to consent on the same day. All consenting procedures are followed for in-person or phone consenting, including: time to review consent, time to ask questions, the patient will not be rushed or coerced, the patient will be informed of the voluntary nature of research, and all other options will be discussed. If the patient chooses to consent to the study, both the patient and consenter will sign the form and the patient will be given a signed copy of the consent forms.

### 6.1.3 Medical history

Review of complete medical, surgical, oncology and psychosocial history via chart abstraction.

### 6.1.4 Concomitant medications

Concomitant medications of interest will be recorded via chart abstraction and patient self-report. Concomitant use of analgesics is permitted if the dose has been stable for at least 2 weeks (no new analgesics have been added, discontinued, or changed in the last 2 weeks). Changes will not be permitted while on-study.

### 6.1.5 Self-reported Pain

Participants will be asked to grade their average neuropathic pain over the last month on a scale of 1-10. The participant may provide their answer verbally, electronically, or on paper.

### 6.1.6 Review subject eligibility criteria

### 6.2 Procedures On-Study

### 6.2.1 On-Study Procedures Prior to Treatment

**T0** (Baseline) – To be completed within 2 weeks of treatment start date Questionnaires can be emailed, mailed, or given in person.

- Concomitant Medications
   All current medications will be abstracted from the medical record review at T0 visit.
- Demographics Questionnaire

Demographic information will be collected via patient report, including gender, age, height, weight, ethnicity, race, marital status, employment status, income level, and highest level of education.

- Total Neuropathy Score clinical (TNSc) Physician or Nurse Assessed
  The TNSc is a 6-item tool that combines patient report of subjective sensory
  and motor symptoms, deep tendon reflexes, manual muscle testing of distal
  muscles, pin sensibility, and quantitative vibration thresholds using a
  Biothesiometer®. Total score ranges from 0-24 points, with higher scores
  indicating worse neuropathy. Timed Up and Go Test (TUG)
  The TUG is a standard test used to assess balance and fall risk. The test
  measures the time taken by an individual to stand up from a standard arm
  chair, walk a 10 feet, turn around, walk back to the chair, and sit down.
- Functional Assessment of Cancer Therapy/Gynecologic Oncology Group – Neurotoxicity (FACT/GOG-NTX), Version 4; Neurotoxicity Subscale Only

The FACT/GOG-NTX Neurotoxicity Subscale is a validated 11-item self-report questionnaire that evaluates symptoms and concerns associated specifically with chemotherapy-induced neuropathy.

 Patient-Reported Outcomes Measurement Information System 29 (PROMIS 29)

PROMIS-29 is a collection of short form instruments which encompass 7 PROMIS domains (depression, anxiety, physical function, pain interference, fatigue, sleep disturbance, and ability to participate in social and activities) in addition to a single item assessing pain intensity. The PROMIS 29 contains 4 items per domain plus one pain intensity item, totaling 29 items. Each domain is scored separately.

Edmonton Symptom Assessment System (ESAS)

The ESAS is a validated, self-administered tool used to screen and measure common symptoms among patients with cancer. It consists of 10-items rated on a numerical scale (0=best, 10=worst) assessing pain, fatigue, nausea, depression, anxiety, drowsiness, shortness of breath, sleep, appetite, and wellbeing. If a patient rates their score in between two numbers, the researchers will round up to the nearest higher number. ESAS scores can be obtained via chart abstraction if completed within visit window.

### Sock Dispensing

Patients on Arm A will be given 6 pairs of Voxx HPT socks along with a start date on when the patient should begin wearing the socks (start date = Day 1). Patients will be asked to wear the socks continuously during both waking and sleeping hours for two weeks from that start date, except when showering, bathing, or swimming.

Patients on Arm B will be given 6 pairs of placebo socks along with a start date on when the patient should begin wearing the socks (start date = Day 1). Patients will be asked to wear the socks continuously during both waking and sleeping hours for two weeks from that start date, except when showering, bathing, or swimming.

Patients will be told that the socks can be washed on delicate cycle and worn repeatedly. Patients will be asked not to let others wear the socks during the course of the trial.

The investigator and patient will be blinded to treatment assignment.

Daily Sock Diary Instruction

Patients will be given the Daily Sock Diary form and asked to keep a daily record of approximately how many hours the socks were worn, and whether the socks were worn while sleeping.

### Day 0 - One Day before Treatment Start Date (-2 days)

 A phone call will be made to the patient to remind them to start wearing their socks the following day (Day 1), and to keep daily records of approximately how many hours the socks were worn.

### **6.2.2 Procedures During Treatment**

### WEEK 1

- Continuous Sock Wearing (Arm A: Voxx HPT Socks; Arm B: Placebo)
- Daily Sock Diary Entries

Patients will be asked to keep a daily record of approximately how many hours the socks were worn, and whether the socks were worn while sleeping.

Reminder Calls

Phone calls will be made to the patients on Day 3 (+/- 2 Days) and Day 7 (+/- 2 days) to remind the patients to wear their socks and to monitor for any adverse events. Thereafter, patients will be able to call a study coordinator with any questions or concerns.

### WEEK 2

- Continuous Sock Wearing
- Daily Sock Diary Entries

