### **WEEK 3 (WASHOUT)**

• T1 – Day 15 (+3 days)

All procedures below are completed for research only.

Concomitant Medications of Interest

Current medications of interest will be abstracted through medical record review at T1 visit.

- TNSc Physician or Nurse Assessed
- o TUG
- Questionnaires (can be emailed, mailed, or given in person)
  - FACT/GOG-NTX v4, Neurotoxicity Subscale
  - PROMIS-29
  - ESAS
- Sock Diary Submission Patients will be asked to submit their daily sock diaries to the coordinator.
- Sock Return Patients will be asked to return all study socks to the study coordinator.
- Sock Dispensing Patients will be given 6 new pairs of socks, according to assigned arm:
  - Patients on Arm A will be given 6 pairs of placebo socks along with a start date on when the patient should begin wearing the socks (start date = Day 29). Patients will be asked to wear the socks continuously during both waking and sleeping hours for two weeks from that start date, except when showering, bathing, or swimming.
  - Patients on Arm B will be given 6 pairs of Voxx HPT socks along with a start date on when the patient should begin wearing the socks (start date = Day 29). Patients will be asked to wear the socks continuously during both waking and sleeping hours for

- two weeks from that start date, except when showering, bathing, or swimming.
- Patients will be reminded that the socks can be washed on delicate cycle and worn repeatedly. Patients will be reminded not to let others wear the socks during the course of the trial.
- The investigator and patient will be blinded to treatment assignment.
- Daily Sock Diary Instruction Patients will be reminded to keep a
  daily record of approximately how many hours the socks were worn
  and to note whether the socks were worn while sleeping.

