### **WEEK 4** (WASHOUT)

• Day 28 – One Day before Crossover Treatment Start Date (-2 days)
A phone call will be made to the patient to remind them to start wearing their socks the following day (Day 29), and to keep daily records of approximately how many hours the socks were worn.

### WEEK 5

- Continuous Sock Wearing
- Daily Sock Diary Entries
- Reminder Calls

Phone calls will be made to the patients on Day 31(+/- 2 Days) and Day 35(+/-2 Days) to remind the patients to wear their socks and to monitor for any adverse events. Thereafter, patients will be able to call a study coordinator with any questions or concerns.

### WEEK 6

- Continuous Sock Wearing
- Daily Sock Diary Entries

Any patient who stops study treatment early will be encouraged to return to the study center for all study visits. The reason(s) for any study or assessment discontinuation will be documented.

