### 6.2.3 T2 (End of Treatment Visit) – Week 7, Day 43 (+3 days)

All procedures below are completed for research only.

- Concomitant Medications of Interest
   Current medications of interest will be abstracted through medical record review at T2 visit.
- TNSc Physician or Nurse Assessed
- TUG
- Questionnaires (can be emailed, mailed, or given in person)
  - FACT/GOG-NTX v4, Neurotoxicity Subscale
  - o PROMIS-29
  - o ESAS
- Sock Return Patients will be asked to return all study socks to the study coordinator.
- Sock Diary Submission Patients will be asked to submit their daily sock diaries to the coordinator.

Time and Events Table

	Screening	T0 (Baseline) within 2 weeks of treatment start date		·	Treatment	rent		*11		Cross	Crossover Treatment	atment	T2* (End of Treatment Visit)
Day			0	1	3	2 8	8-14	15	28	29 31	1 35	36-42	43
Week				1	  -	  -	2	3	4	5 2	2	9	7
Informed Consent	×					 	$\vdash$			L	L		
Medical History	×			Г	Г	H	Н			L	L	L	
Concomitant Medications of Interest	×	×		Г	Г	H	Н	×		L	L	L	×
Pain Assessment (Self-Report)	×			Г	H	H	H			L	L	L	
Assessment of Eligibility	×			Г	Г	L	Н		Г	L	L		
Demographics Questionnaire		×		Γ	┢	H	┝			L	L	L	
TNSc (Physician or Nurse Assessed)		×				L	$\vdash$	×	_	L	L		×
TUG		×		Γ	F	L	H	×	Г	L	L	L	×
FACT/GOG-NTX – Neurotoxicity Subscale		×						×					×
PROMIS-29		×			H	L	Н	×		L	L	L	×
ESAS		×				_		×					×
Socks Dispensed to Patients		×		_		_		×					
Socks Returned by Patients				_		_		×					×
Treatment Implementation				Contir	Continuous Sock Wearing; See Section 6	ck Weari tion 6	.Bc:	WASHOUT PERIOD	TUC OC	Continuc	Continuous Sock Wearing; See Section 6	Wearing; າ 6	
Sock Diary Entries					Daily Entries	ıtries	Н		П	Ö	Daily Entries	ses	
Sock Diary Submission							Н	×	Н		L		×
Patient Reminder Phone Calls			×		×	×			××	×	×		
Adverse Event Monitoring					×	×	Н	Н		×	×		

\*Time point has a +3 day window ^Day 0 and Day 28 reminder calls have a -2 day window X $^1$  Day 3, Day 7, Day 31 and Day 35 reminder calls have a  $\pm 2$  day window

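### Adverse events are asked about on schedule only at the Day 3, 7, 31 and 35 calls, so the second week of wear has late enquiry in Period 1 and none in Period 2

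*Combined protocol and SAP*

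**What the plan says.** Section 6.2.2 (Week 1) places AE monitoring in the reminder calls on Day 3 and on "Day 7 (+/- 2 days) to remind the patients to wear their socks and to monitor for any adverse events". Section 6.2.2 (Week 5) does the same for Day 31 and "Day 35(+/-2 Days) to remind the patients to wear their socks and to monitor for any adverse events". After each pair of calls, contact is left to the patient: "Thereafter, patients will be able to call a study coordinator with any questions or concerns".

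The T1 list (Section 6.2.2, Week 3) and the T2 list (Section 6.2.3) cover medications, TNSc, TUG, three questionnaires, diary submission and sock return, plus dispensing at T1. At both visits, "Patients will be asked to return all study socks to the study coordinator". Neither list has an AE item. The Day 28 call is a reminder about wear and the diary only. For T1 and T2 the events table notes "Time point has a +3 day window". Its AE row has four marks, which agrees with the four calls.

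Section 7.1 says that patients will be watched for skin irritation and discomfort from the socks, and that only intervention-related events are recorded. Section 7.2.1 names three expected events: irritated skin, foot or ankle discomfort, and a brief mild rise in foot pain in the first three days of wear. Section 7.3 Step 4 names only the first two.

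**The concern.** Each sock is worn for two weeks, day and night, but scheduled questions about reactions stop about halfway through each period. The two periods then differ. A reaction in the second week of Period 1 is next asked about after the crossover, with the other sock on. A reaction in the second week of Period 2 is not asked about again, although the patient is seen the day after wear nominally ends.

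Attribution matters because Section 7.1 makes relatedness the condition for recording an event, and because it says the data also serve people in later studies of similar products. For that purpose an event has to be tied to the sock that caused it. The Day 31 call is poorly placed for this. It nominally falls on the third day of the new sock, inside the three days in which Section 7.2.1 expects transient foot pain, so an old complaint and a new one are easily confused.

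The other planned data collection does not fill the gap for skin reactions. In the diary patients "keep a daily record of approximately how many hours the socks were worn, and whether the socks were worn while sleeping". The FACT/GOG-NTX subscale "evaluates symptoms and concerns associated specifically with chemotherapy-induced neuropathy". The ESAS is described as "assessing pain, fatigue, nausea, depression, anxiety, drowsiness, shortness of breath, sleep, appetite, and wellbeing". Section 6.2.1 describes no skin item in these, in PROMIS-29 or in the TNSc.

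**Working it through.** The plan states no figure on this point, so there is none to reproduce. The check is day counting.

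**Inputs**
- Wear days: 1–14 and 29–42, 28 in total (Sections 6.2.1 and 6.2.2).
- Last Period 1 call: Day 7, window 5–9. First Period 2 call: Day 31, window 29–33. Last Period 2 call: Day 35, window 33–37 (Section 6.2.2).
- T1: Days 15–18. T2: Days 43–46 (Sections 6.2.2 and 6.2.3).

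**1. Wear days after the last enquiry of the period** = last wear day − day of last call.
- Period 1: 14 − 7 = 7; range 14 − 9 = 5 to 14 − 5 = 9.
- Period 2: 42 − 35 = 7; range 42 − 37 = 5 to 42 − 33 = 9.
- Period 2 days as a share of all wear days: 7/28 = 25%; range 5/28 = 18% to 9/28 = 32%.

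**2. Gap from the last Period 1 enquiry to the next one** = 31 − 7 = 24 days; range 29 − 9 = 20 to 33 − 5 = 28.

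**3. Age of a late Period 1 event when first asked about** = day of call − day of event.
- Nominal: 31 − 14 = 17 to 31 − 8 = 23 days.
- Over the windows: 29 − 14 = 15 to 33 − 6 = 27 days. The maximum takes the Day 7 call as made on Day 5 and the event on Day 6.

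**4. Wear day of the second sock at that call** = day of call − 28. Nominal 31 − 28 = 3; range 29 − 28 = 1 to 33 − 28 = 5. Even the earliest permitted call falls when the other sock is on. Calls on Days 29–31 fall within the first three wear days; calls on Days 32–33 do not.

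**5. With an AE question at T1 and T2**
- Age of a late Period 1 event: nominal 15 − 14 = 1 to 15 − 8 = 7 days; maximum 18 − 6 = 12.
- Age of a late Period 2 event: nominal 43 − 42 = 1 to 43 − 36 = 7 days; maximum 46 − 34 = 12.
- From T1 to the start of the second sock: 29 − 18 = 11 to 29 − 15 = 14 days.

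| | Current plan | With T1 and T2 questions |
|---|---|---|
| Late Period 1 event: age when first asked about | 17–23 days (15–27) | 1–7 days (1–12) |
| Late Period 2 event: age when first asked about | no later scheduled enquiry | 1–7 days (1–12) |
| Wear days with no later enquiry, of 28 | 7 (5–9) | 0 |
| Sock worn when Period 1 is asked about | the other sock | none (washout) |

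The column alignment of the events table could not be relied on, so these results rest on the procedure text; the table's four AE marks agree with it.

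**The case against.** The strongest reply is that this is a deliberate and proportionate design. The product is a commercially available sock, Section 7.1 regards AEs as very unlikely, and the only expected event with a stated time course occurs in the first three days, which the calls target. There are other routes to a report:
- patients may phone in;
- early stoppers are encouraged to attend visits and their reasons are documented (Sections 6.2.2 and 6.4);
- the investigator reviews study data continuously (Section 9.5.2);
- serious events that staff learn of must be reported up to the end-of-treatment visit (Section 7.4.1);
- the note in Section 7.3 covers events up to 30 days after last treatment;
- a clinician performs the TNSc at T1 and T2, and the pain items may bring foot pain to light.

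AEs are also not an endpoint, and Section 8.0 plans no comparison of them by sock.

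Much of this stands. It narrows the gap to mild events that the patient does not volunteer. It also means that 25% is a share of wear days, not of events; the documents give no rate or timing for later reactions. Section 7.1 sets no timing that the schedule breaks, so there is no outright contradiction.

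It does not remove the gap. None of these routes is a scheduled AE question, and none specifically asks about skin. The low expected risk argues for a light remedy, and the remedy here is light.

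**Conclusion.** The concern holds. Followed exactly, the plan leaves nominally half of each wear period (5 to 9 of 14 days over the windows) without an AE enquiry before the crossover or before the end of the study. In Period 1 the enquiry is 15 to 27 days late and made under the other sock; in Period 2 it does not come at all.

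The conclusion rests on three assumptions. The T1 and T2 lists are taken as complete. The diary and questionnaires are taken to contain what Section 6.2.1 describes. The Day 31 call is assumed to look back to Period 1, which Section 6.2.2 does not state; if it does not look back, late Period 1 days also have no later enquiry.

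What is at stake is non-serious reactions, above all skin irritation, and their attribution to the right sock. This is a change the sponsor should make, not a flaw that threatens the trial. The differing lists of expected events in Sections 7.2.1 and 7.3 are a separate, minor matter.

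**What to change.** Add one AE question, with date of onset, to the T1 visit before the second socks are dispensed, and one to the T2 visit. Mark both in the AE row of the events table and cross-refer to them in Section 7.1. Both visits already take place, with a clinician assessment and the return of the socks, so no visit or call is added. The cost is a minor amendment and slightly more data collection. A T2 question would not reach the rest of the 30-day period mentioned in Section 7.3 (to Day 42 + 30 = 72); that would still depend on patients reporting for themselves.

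Separately, reconcile the expected-event lists in Sections 7.2.1 and 7.3 Step 4 into one list, with the content decided by the sponsor.
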